## **Comparison**

All families will be offered Usual Care (UC): the trial arms will be differentiated by whether or not MB (or in the add-on study: MBO) is made available. UC will include normal care from the health visiting team and from the general practitioner (GP), and in some cases a social worker or paediatric team. Where required, referral to additional services (hospital-, local authority- or third sector-based services) will take place. The nature of UC will be varied and could include simple practical support (helping mother at home) and advice (suggesting behaviour management strategies), individual psychotherapeutic support such as cognitive behaviour therapy, pharmaceutical intervention such as anti-depressant medication, assessment and intervention in child behaviour problems. The full range of types of UC and potential impact will be explored within the process evaluation.

Although UC is potentially complex and could include other parenting interventions, we have consulted with HV and GP colleagues and it is clear that restricting UC to families in either arm of the trial would be considered unethical. Currently standard care would include scheduled HV visits at 8 months, 13-15 months and 27-30 months but with no formal assessment of maternal or child mental health (53). Following these visits HVs use their professional judgement to decide whether to revisit or to refer onwards to other services. Around 15- 20% of all families receive additional unscheduled visits between 12 and 30 months, and the proportion is likely to be higher in participants eligible for this trial. Patterns of visits to GPs for support vary between families but we have recently published papers based on routine data (54) and on parent-reported data from the Growing Up in Scotland (GUS) cohort (55). Typically, a family will consult a GP 3-4 times per year with a child between 13 and 30 months: in the GUS study, 6.1% of families reported using a GP and 17.8% a HV for information about children's behaviour in the third year of life. It is noteworthy that the control arm of the recently published evaluation of the Family-Nurse Partnership (56) received eight more HV visits than the intervention arm.

We intend to characterise the nature of UC at the first follow up contact (8 months post randomisation) through a brief questionnaire to the HV and to the parent. We shall also review GP and health visitor records when the child is 30 months old to assess use of primary and secondary care services and the nature of any therapeutic interventions.

## **4. TRIAL RECRUITMENT**

### **4.1 Trial population**

Anxious or depressed mothers with principal caregiving responsibilities who have a child between 6 and 18 months living in the Highland Council region (where 34% of the population are in the urban centre of Inverness, and a further 35% within an hour's drive). Potential participants will be identified by HVs, GPs, social workers or paediatricians. Referred mothers will be asked to complete the HADS (57) by telephone, found to be a useful method in similar studies (58, 59). We aim to recruit families where the maternal score on the HADS exceeds either 10 on the Anxiety subscale or 6 on the Depression subscale, corresponding to the 85th centile for the UK female population (60).

We aim to recruit 212 families to achieve evaluable data on 170. Given the strong health service and local authority management support for this trial, recruitment of around 3 families per week should be achievable. We calculate that the standard deviation of the total HADS score in this population will be approximately 7 points: in a normative population female sample the mean score is 10 points and SD 6 points (60). In a study using HADS as an outcome measure in a population similar to our proposed sample, mean change scores were 8.13 (SD 6.61) (61). The final sample size of 170 will give us 90% power to detect an effect size of 0.5 in the maternal HADS, corresponding to approximately 3 points. Although a Minimal Clinically Important

Difference has not been clearly stated for the HADS (62), 3 points is likely to represent a clinically significant reduction based on the results of the Livingstone et al trial (61).

Mellow Babies Online (MBO) will recruit a remote and rural population (i.e. those who will not be able to participate in the main trial due to location). The study population will also include those who would struggle to attend in-person groups regardless of location (e.g. those with symptoms of social anxiety, other health challenges or caring responsibilities). For this add-on study, we aim to recruit 32 families.

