## **9. SAMPLE SIZE AND PROPOSED RECRUITMENT RATE**

### **9.1 Sample size**

We plan to recruit 212 participants, aiming to obtain evaluable data on 170. Randomisation will be 1:1. A sample size of 85 per group will give us 90% power at 5% significance to detect an effect size of 0.5. This corresponds to a score of around three points on the HADS, which is likely to represent a clinically significant improvement (61). We shall use a minimisation design to reduce imbalance between groups in terms of maternal age (<25; ≥25), deprivation (working household yes/no) and age of child (≤12 months; >12 months). In terms of secondary child-based outcomes, we shall have approximately 80% power to detect an effect size of 0.4 at 5% significance after adjusting for baseline covariates. We have allowed for 20% attrition which is broadly in line with clinical and evaluation experience, and several design features (e.g., telephone collection of outcome data) will increase follow up rates.

For the MBO add-on study we plan to recruit 32 participants (16 per arm). No formal sample size calculation is needed as this add-on study aims only to establish feasibility of evaluating MBO in a definitive trial.

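### At the protocol's own SD of 7, an effect size of 0.5 is 3.5 HADS points, not about 3; 85 mothers per arm give about 79% power for 3 points, not 90%

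*Protocol*

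**What the plan says.** Protocol Section 4.1 states that "the standard deviation of the total HADS score in this population will be approximately 7 points". The same paragraph gives two other values: SD 6 in a normative female sample, and SD 6.61 for change scores in a study of a population described as similar. It then claims 90% power at 170 evaluable participants to "detect an effect size of 0.5 in the maternal HADS, corresponding to approximately 3 points", and argues that 3 points is probably a clinically significant reduction.

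Section 9.1 states: "A sample size of 85 per group will give us 90% power at 5% significance to detect an effect size of 0.5". It continues: "This corresponds to a score of around three points on the HADS", and again rests clinical significance on that figure. For the child outcomes it says that "we shall have approximately 80% power to detect an effect size of 0.4 at 5% significance after adjusting for baseline covariates".

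Section 10 plans to adjust for baseline covariates, including the baseline of the outcome, and to fit therapy group as a random effect in the active arm. It expects the adjustment to recover power lost to clustering. Its examples are a correlation just over 0.2 to offset a 5% increase in required sample size, and just over 0.3 to offset 10%.

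Section 20 (close-down plan) says that the trial will be underpowered and that no effectiveness analysis will be done.

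**The concern.** The protocol states the target difference on two scales that disagree. In standard deviation units it is 0.5; in points it is about 3. With the SD expected for this population, those are different targets, and the stated power belongs to only one of them. The argument for clinical relevance is made in points, so the figure a reader will take away, 90% power for 3 points, is the one that does not follow.

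The child-outcome statement raises a smaller question. It relies on covariate adjustment to reach about 80% power without saying how strong the covariates must be, while Section 10 uses the same adjustment to pay for clustering.

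What is at stake is the accuracy of the sample-size rationale. A draft final report and a manuscript are planned (Section 20). Anyone who reused 85 per arm as sufficient for 3 points at SD 7 would plan on too few mothers.

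**Working it through.** **Inputs.** 85 evaluable per arm, 1:1, 5% significance, effect sizes 0.5 and 0.4, and 20% attrition (Section 9.1); SDs of 7, 6.61 and 6 points (Section 4.1); illustrative clustering inflation of 5% and 10% (Section 10). Sidedness is not stated. I assume two-sided, which reproduces the protocol's figure.

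**Method.** Two-sample t-test: d = difference / SD, noncentrality d × √(n/2), 2n − 2 degrees of freedom. Covariates with correlation r to the outcome multiply the variance by (1 − r²); clustering multiplies it by the inflation factor.

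**The protocol's own figure.** n = 85, d = 0.5: noncentrality 0.5 × √42.5 = 3.26, power 90.0%. The standardised statement is correct.

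**Conversion to points.** 0.5 × 7 = 3.5; 0.5 × 6.61 = 3.3; 0.5 × 6 = 3.0.

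**Power at 85 per arm, unadjusted and ignoring clustering.**

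| Difference | SD | d | Power |
|---|---|---|---|
| 3.5 points | 7 | 0.500 | 90.0% |
| 3 points | 6 | 0.500 | 90.0% |
| 3 points | 6.61 | 0.454 | 83.7% |
| 3 points | 7 | 0.429 | 79.3% |

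The normal approximation gives 79.8% for the last row. The type II error for 3 points at SD 7 is therefore about 21%, against the stated 10%.

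**Sample size for 3 points at SD 7.** 90% power needs 116 per arm (115 by the normal approximation). That is 232 evaluable, or 232 / 0.8 = 290 recruited. The planned 85 is 85 / 116 = 73% of this, about a quarter too few.

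**Could adjustment restore 90% for 3 points?** At 85 per arm, 90% power needs d of about 0.500. The condition is 1 − r² = (0.4286 / 0.500)² = 0.734, so r is about 0.52 before any clustering. If the same adjustment must also absorb 5% or 10% inflation, r is √(1 − 0.734/1.05) = 0.55 or √(1 − 0.734/1.10) = 0.58.

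**Child outcomes at d = 0.4.** Unadjusted power is 73.7%. The effect detectable with 80% power is 0.432. The condition is 1 − r² = (0.4 / 0.432)² = 0.857, so r is about 0.38 with no clustering. At r = 0.30 power is 77.6%. If the adjustment must also offset clustering:
- 5% inflation: r = √(1 − 0.857/1.05) = 0.43
- 10% inflation: r = √(1 − 0.857/1.10) = 0.47

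These are total correlations. Variance factors multiply, so the correlation needed for clustering and the one needed for 80% power cannot simply be added.

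**The case against.** The strongest reply has three parts.

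**The power claim is attached to the effect size, and that claim is right.** This stands: 90% for 0.5 reproduces. But calling the points figure loose rounding does not remove the problem. Half of 7 is exactly 3.5, and the gap between 3 and 3.5 is worth about 11 percentage points of power. The protocol makes its clinical argument on the 3.

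**The planned analysis adjusts for baseline HADS, so the residual SD matters more than the raw SD of 7.** This is correct in principle. At r = 0.5 the residual SD is 6.06 and power for 3 points is 89.4%; at r = 0.4 it is 85.8%. However, the protocol states no such correlation, does not use adjustment to support the 3-point figure, and in Section 10 applies the gain to clustering with example correlations of only just over 0.2 and 0.3.

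**The child-outcome figure is expressly conditional on adjustment.** This stands too. A reader might infer that the plan has no covariate gain for the child outcomes, because Table 1 shows no baseline SDQ, SSLM or Bayley/ASQ. The documents do not support that. BITSEA has its own baseline, child age is a minimisation factor, baseline BITSEA and HADS can serve as predictors, and Section 10 plans similar models for secondary outcomes. A correlation of 0.3 already gives about 78%. What remains is that no correlation is stated and the same gain is relied on in two places.

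Finally, the trial is closing and no effectiveness analysis will be run. That limits the consequence to the written rationale.

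**Conclusion.** The concern holds for the HADS conversion. At the protocol's SD of about 7, an effect size of 0.5 is 3.5 points. With 85 per arm and a two-sided 5% test, power for 3 points is about 79% at SD 7 and 84% at SD 6.61; it reaches 90% only at SD 6, or with a covariate-outcome correlation of about 0.52 that the protocol does not claim. These figures are unadjusted and ignore clustering.

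For the child outcomes only a narrower point holds. The figure of about 80% is attainable, but it depends on an unstated correlation: about 0.38 without clustering, or 0.43 to 0.47 in total if the adjustment also offsets the 5% to 10% inflation in Section 10. I give no clustered power figure, because the documents state neither an intracluster correlation nor a group size.

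A reader might also infer that a pending result or decision is compromised. It is not: Sections 20 and 20.2 cancel the effectiveness analyses, so the error lies in the stated rationale alone.

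**What to change.** Leave the sample size as it is. In Sections 4.1 and 9.1, and wherever the sample-size rationale is reported, replace the conversion with wording such as: *85 per arm gives 90% power for 3.5 HADS points (0.5 SD, SD 7) and about 79% for 3 points, before covariate adjustment and clustering.*

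In Section 9.1, add the condition on the child outcomes: *Power at 0.4 SD is 74% unadjusted; 80% requires a covariate-outcome correlation of about 0.38 ignoring clustering, or about 0.43 to 0.47 in total if the same adjustment must also offset a 5% to 10% clustering inflation.*

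The cost is a few sentences and a less favourable stated power for 3 points. Recruitment, conduct and the remaining analyses are unaffected.

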## 4.2 Inclusion and exclusion criteria

### ***Inclusion criteria:***

- (i) mothers with principal caregiving responsibilities scoring  $\geq 11$  on HADS-A or  $\geq 7$  on HADS-D
- (ii) with a child who will be aged 6-18 months at the time of randomisation
- (iii) living in Highland Council region

### ***Exclusion criteria:***

- (i) Current substance dependence
- (ii) Inability to complete questionnaires or participate in groups because of limited English language comprehension
- (iii) Child with learning difficulties sufficient to make outcome assessment impossible
- (iv) Mother has already participated in the trial (e.g., second eligible baby within life of the study)
- (v) Mother under aged 16 years
- (vi) Mother of twins or other multiple births who would otherwise be of eligible age to take part in the study

Participants in the MBO add-on study will meet the same inclusion/exclusion criteria as those in the MB trial but will face additional barriers to in-person groups.

MBO participants will reside in remote and rural areas out with the capacity of the main trial and/or will have other significant challenges to attending in-person groups (e.g. symptoms of social anxiety, other health challenges or caring responsibilities).

## 4.3 Identifying and approaching participants

Referrals will be made by health visitors, social workers, GP or paediatricians with concerns about the relationship between a mother and her child aged 6-18 months. Referrals may also be made by nurseries and third sector organisations, whereby staff within these organisations will act as a referrer and have the ability to provide the mother with information about the study, before providing her with an EoI form so she can then be contacted by the study's research nurse if she is interested in taking part in the trial.

Alongside the acceptance of referrals from referring practitioners, both health professionals and third sector organisations, potential participants may also self-refer. Recruitment posters will be displayed around the community (e.g. libraries, shopping centre's display boards) and in locations where mothers and babies may gather (e.g. mother and toddler groups). Posters will also be displayed in GP and hospital waiting rooms. Through the use of social media recruitment posters will also be displayed on the trial Facebook page.

The trial team will also utilise a number of additional recruitment methods in order to maximise potential participant figures. The following methods will be noted below:

### **1. Increased presence in the community**

Coffee mornings will be hosted by the trial team in central community locations that are easily accessible for mothers with young children. The aim of the coffee mornings will be to provide information about the trial and answer any questions mothers may have about their eligibility for the trial, or what participating in the trial may involve. The trial team also intends to begin attending local mother and toddler groups.

As a way to engage the public, the trial team also intend to host a mini-series of events, that will showcase the work being conducted by our partners NHS Highland Research Development and Innovation department, as well as providing more information to the public regarding the Mellow Babies Trial. In all cases it is hoped that by increasing our presence in the community, it will increase public awareness of the trial, which will subsequently increase participant numbers.

## **2. The use of Participant Identification Centre (PIC) sites**

It has been highlighted to the trial team by the former Director of Public Health of NHS Highland, [name] [name], that the use of PIC sites with the support of the Public Health department may also increase participant numbers. [name] has provided assurances that this procedure is completely ethical. An invitation letter (included amendment submission AM07) would be sent to any potential participants who fit the trial's eligibility criteria. Any interested participants would then be provided the relevant contact details should they wish to express interest in participating in the Mellow Babies Trial.

We will send out these PIC letters using the mail communication service Docmail ([www.cfhdocmail.com](http://www.cfhdocmail.com)). The addresses of potential participants will be accessed through Public Health records by a member of the research team under an honorary contract with Public Health and holding a Research Passport. Having an honorary contract with NHS Highland negates the need for a research passport. Participant names and addresses will then be uploaded to Docmail in an excel spreadsheet, along with the invitation letter, an expression of interest form and a response envelope. Docmail will then print and post out letters to all participants. Docmail has been used for patient communication by the NHS for over 12 years, and is an approved supplier on NHS Digital and procurement boards. It is GDPR compliant, accredited by the Data Security and Information Toolkit, and Cyber Essential Plus certified.

Given the success of the PIC sites (3% response rate), it is intended that the trial team also send out a follow-up letter to those parents who have received an initial PIC invitation and who still have babies in the eligible age range. This follow-up letter will act as a reminder and invite potential eligible mothers to get in touch with the trial team if they are interested in taking part in the trial (follow-up letter included in amendment submission AM013). We will also send out these follow-up letters using Docmail.

MBO participants will be recruited in a similar manner as Mellow Babies Trial participants. Potential participants will self-refer or be referred by health professionals (e.g. health visitors) and third-sector organisations. PIC letters will be the main recruitment strategy, along with social media advertisement of MBO. PIC letters will highlight the opportunity to join an online – rather than in-person – group should prospective participants be living in remote areas where attending (and feasibly running) an in-person group would be difficult or impossible (AM021). PIC letters will also highlight the opportunity for mothers to contact the study team to discuss MBO if they feel unable to attend face-to-face groups, regardless of location.

## **3. The use of vignettes**

It is intended that anonymised vignettes from current participating mothers, both in the control and intervention arm of the trial, will be used to illustrate what it is like to take part in the trial. We hope that using this material may encourage other mothers to come

forward and express interest in participating in the trial. To reiterate, these vignettes will be anonymised and will only be used if the participating mother has given consent.

With this in mind, new consent forms will be developed to capture the use of vignettes for the trial. This will be included in the 'optional' section of the consent form (new consent forms can be found in amendment AM013). During follow-up visits (at 8-months post randomisation and when the participating child is 30-months old) we will ask mothers who gave consent using (2-086-18 Mellow Babies consent v1 17Sept18) if they wish to sign the amended consent form (2-086-18 Mellow Babies consent v2 13March20) in order to provide an anonymised vignette, they may do so.

The referrer will briefly describe the MB study to the mother and ask her to complete an Expression of Interest (Eoi) form including her preferred contact details to be passed to the Study's Research Nurse at the Highland Clinical Research Facility (HCRF). We will also allow a form of self-referral via PIC letter where the mother returns the Eoi by post or expresses interest by contacting the HCRF nurse via phone or email. Self-referrals are also accepted where practitioners provide a study flyer (including the Eoi form) to potential participants, and they may contact the Study's Research Nurse directly. We also plan to use social media to publicise the study and include contact information for the HCRF research nurse who is taking referrals to the study.

The Research Nurse will telephone the mother to seek permission to send her the PIL and a Consent for Screening form. She will also make an appointment to call back and run through the HADS questionnaire within the following week (where feasible). Repeated attempts will be made where appointments are not kept, for up to one month, or if the baby reaches 18 months of age (and therefore moves out of eligible range).

The referral process for MBO is similar to that of the Mellow Babies Trial. The referrer will briefly describe the MB study (including the option of MBO) to the mother and ask her to complete an Expression of Interest (Eoi) form including her preferred contact details to be passed to the HCRF Research Nurse. We will also allow a form of self-referral via PIC letter where the mother returns the Eoi by post or expresses interest by contacting the HCRF research nurse directly via phone or email. Self-referrals are also accepted where practitioners provide a study flyer (including the Eoi form) to potential participants, and they may contact the study's Research Nurse directly. As of AM021 this Eoi form highlights the opportunity to take part in Mellow Babies Online. We also plan to use social media to publicise the study and include contact information for the HCRF Research Nurse who is taking initial referrals to the study.

Any mothers who have expressed an interest in taking part in the Mellow Babies Trial, but who have been identified by the HCRF Research Nurse as unable to attend in-person MB groups due to challenges related to remote and rural living, will be asked whether they would want to take part in the MBO study instead. Potential participants for whom in-person groups are inaccessible regardless of location (e.g. those with additional caring responsibilities, health challenges or who experience symptoms of social anxiety) will also be asked if they would like to take part in MBO. If interested in MBO the Research Nurse at HCRF will ask for permission to pass the potential participants contact details to the UoA researchers involved in the MBO add-on study for future contact. A UoA researcher will contact the potential participant to conduct the screening process, providing more information about the MBO study and assessing eligibility for participation using the HADS.

